# 5.5 Withdrawal Criteria (if applicable)

Subjects may voluntarily withdraw from the trial at any time. Additionally, subjects may be discontinued for safety reasons as determined by the investigator and/or Medical Monitor.

#### 6 STUDY PARAMETERS

#### 6.1 Primary Endpoint

- Schirmer's Test overall mean change from baseline (CFB) before and after the fourth dose on Day 1
- Schirmer's Test greater than or equal to 10mm responder analysis of change from baseline before and after the fourth dose on Day 1

#### **6.2** Safety Endpoints

Visual acuity

Confidential Page 21 of 60

- Slit-lamp evaluation
- Adverse event query
- Intraocular Pressure (IOP)
- Dilated fundoscopy

# **6.3** Secondary Endpoints

- Overall mean CFB of Conjunctival Redness over 90 minutes in the CAE at Day 2
- Overall mean CFB of Eye Dryness (VAS; Visual Analog Scale) over 90 minutes in the CAE at Day 2
- Overall mean CFB of Eye Dryness (VAS) assessed over Days 1 and 2 (excluding CAE)

Confidential Page 22 of 60

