#### 4 OVERALL STUDY DESIGN

ADX-102-DED-023 is a Phase 3, multi-center, randomized, double-masked, parallel design, vehicle-controlled trial designed to evaluate the efficacy and safety of 0.25% Reproxalap Ophthalmic Solution compared to vehicle in subjects with dry eye disease. Approximately 350 subjects will be enrolled in the study. Male and female subjects at least 18 years of age with a subject-reported history of dry eye disease in both eyes and meeting all other eligibility criteria will be randomized to receive reproxalap or vehicle in a 1:1 ratio (approximately 150 subjects in each treatment group).

Visit 1 (Day -14 -16/+ 2): Screening	
 
Informed Consent
 
Demographics, Medical/Medication & Ocular History
 
Urine Pregnancy Testing (as needed)
 
Symptom Questionnaires, Ocular Dryness VAS, Visual Acuity
 
Slit Lamp Exam with Conjunctival Redness assessment
 
CAE exposure (90 minutes) with Ocular Dryness VAS, and Conjunctival Redness Assessment
 
Slit Lamp Exam with Conjunctival Redness assessment
 
Schirmer's Test
 
IOP and Dilated Fundoscopy
 

Visit 2 (Day 1): Randomization/Baseline	
 
Medical/Medication Update: AE Query
 
Visual Acuity
 
Slit Lamp Exam
 
Symptom Questionnaires at specified time points
 
Conjunctival Redness at specified time points
 
In-Office Doses (QID)
 
Tear Collection & Schirmer's Test at specified time points
 

Visit 3 (Day 2): CAE	
 
Medical/Medication Update: AE Query
 
Urine Pregnancy Testing (as needed)
 
Visual Acuity, Slit Lamp Exam
 
Symptom Questionnaires
 
Conjunctival Redness at specified time points
 

Confidential Page 18 of 60

CAE exposure (90 minutes) with Ocular Dryness
VAS, and and
Conjunctival Redness Assessments
Tear Collection at specified time points
IOP and Dilated Fundoscopy
Study Exit

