#### Visit 2 (Day 1, Baseline and In-Office Dosing)

- Medical/Medication Update
- Adverse Event Query
- Visual Acuity (ETDRS)
- Slit Lamp Biomicroscopy
- Symptom Questionnaires
- Conjunctival Redness Photography
- Inclusion/Exclusion Criteria Review
- Randomization/Enrollment
- Pre-Dose #1 Tear Collection (30 +/- 5 minutes pre-dose)
- In-Office Dose #1
- Post-Dose #1 Tear Collection (started within 10 + 2 minutes of dose) *Wait 3 hours between doses*

Confidential Page 26 of 60

- Pre-Dose #2 Tear Collection (30 +/- 5 minutes pre-dose)
- In-Office Dose # 2
- Post-Dose #2 Tear Collection (started within 10 + 2 minutes of dose) Wait 30 minutes between doses
- In-Office Dose #3
- Conjunctival Redness Photography (10 minutes +/- 2 minutes post-Dose #3)
- Symptom Questionnaires started within 10 minutes + 2 minutes post-

Wait 30 minutes between doses

- Pre-Dose #4 Schirmer's Test (10 +/- 2 minutes pre-dose)
  - Weigh Schirmer's Test strip before and after use
- In-Office Dose #4
- Post-Dose #4 Schirmer's Test (started within 5 +/- 2 minutes of dose)
  - Weigh Schirmer's Test strip before and after use
- Schedule for Visit 3

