# Visit 3 (Day 2, CAE■)

- Medical/Medication Update
- Adverse Event Query
- Urine Pregnancy Test (as needed)
- Visual Acuity (ETDRS)
- Slit Lamp Biomicroscopy
- Conjunctival Redness Photography
- Symptom Questionnaires:

- Pre-Dose #1 Tear Collection (30 +/- 5 minutes pre-dose)
- In-Office Dose #1 within 10 minutes prior to CAE Entry
- CAE Exposure (90 minutes) with:

Confidential Page 27 of 60

- In-Office Dose #2 (45 +/- 2 minutes into CAE exposure, administer by site staff)
- Post-CAE exit Tear Collection (started within 5 + 2 minutes)
- In-Office Dose #3 (started within 2 minutes post-tear collection)
- Symptom Questionnaires started within 10 minutes + 2 minutes post-Dose #3:

- Post-Dose #3 Tear Collection (started within 15 + 2 minutes of dose)
- Slit Lamp Biomicroscopy
- Intraocular Pressure
- Dilated Exam
- Study Exit

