#### **10.2** Statistical Hypotheses

#### 10.4 Statistical Analysis

#### 10.4.1 General Considerations

Quantitative variables will be summarized descriptively using number of subjects (n), mean, standard deviation, median, minimum, and maximum. Qualitative variables will be summarized using counts and percentages.

All summaries will be presented by treatment group. Summaries will be provided for demographics, baseline medical history, concurrent therapies, and subject disposition.

For the purpose of summarization, medical history, concurrent therapies, and adverse events will be coded to MedDRA and WHODrug dictionaries, as appropriate.

Baseline measures are defined as the last non-missing measure prior to the initiation of randomized study treatment at Day 1. Change from baseline will be calculated as follow-up visit value minus baseline value. Treatment comparisons between active and vehicle calculated as active minus vehicle.

Confidential Page 35 of 60

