10.4.2 Unit of Analysis

All analyses will be 2-sided at a significance level of 0.05. 95% confidence intervals will be provided where appropriate.

The statistical analysis plan (SAP) will detail the statistical procedures, and will dominate any text herein.

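### Do the two CAE secondary endpoints waste precision by ignoring the untreated Visit 1 CAE?

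*Combined protocol and SAP*

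**What the plan says.** Protocol section 6.3 lists "Overall mean CFB of Conjunctival Redness over 90 minutes in the CAE at Day 2" and "Overall mean CFB of Eye Dryness (VAS; Visual Analog Scale) over 90 minutes in the CAE at Day 2". They stand third and fourth in the fixed sequence (Synopsis and section 10.4.4), which stops at the first P-value of 0.05 or more.

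Section 10.4.1 gives one general rule: "Baseline measures are defined as the last non-missing measure prior to the initiation of randomized study treatment at Day 1". Change is the follow-up value minus baseline, and the treatment comparison is active minus vehicle.

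In section 8.3.1, Visit 2 lists symptom questionnaires and "Conjunctival Redness Photography" ahead of randomization and the first dose, with no CAE that day. Section 4 gives Visit 1 a "CAE exposure (90 minutes) with Ocular Dryness VAS, and Conjunctival Redness Assessment" before any study drug. Visit 3 repeats a 90-minute CAE with study drug given shortly before entry and again about halfway through.

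The table of contents lists 10.4.5 (primary), 10.4.7 (secondary) and 10.4.8 (exploratory efficacy analyses). In the body, the pages between the endpoint list in 10.4.4 and section 10.4.9 hold almost nothing but page footers and a stray estimand label. The Synopsis and section 10.4.2 both say the SAP overrides the protocol's statistical text. No SAP text is in the released file.

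**The concern.** The rule in 10.4.1 picks the latest pre-treatment value, which for these two measures is the in-office reading on Day 1. The outcome is an average inside the chamber. Change from baseline therefore contains the subject's response to the chamber as well as any treatment effect, and the in-office value may predict that response poorly. Visit 1 supplies what looks like the natural comparator: the same subject, untreated, in a 90-minute CAE, with the same two measures recorded.

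If the models for tests 3 and 4 ignored those readings, the confidence intervals could be wider than necessary. Because the sequence halts at the first failure, a miss on test 3 would also make test 4 and everything after it exploratory. The data are already collected, so the loss would be avoidable.

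**Working it through.** **1. What the text shows about the model.** The visible baseline rule does lead to an in-office Day 1 baseline for both endpoints. A loss of precision needs a second fact, namely that the Visit 1 CAE is not a covariate. Section 10.4.1 is silent on covariates. The section that would state them, 10.4.7, has its heading in the contents and its text withheld, and the governing SAP is not in the file. Withheld text is not evidence of omission. Equally, nothing visible says that the in-office value is itself a covariate.

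**2. Whether the in-office baseline biases the comparison.** Write Y for the Day 2 CAE mean and B for the Day 1 value. The difference in mean change is

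(mean Y, active − mean Y, vehicle) − (mean B, active − mean B, vehicle).

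B precedes randomization, so the second bracket has expectation zero. The response to the chamber that would occur on vehicle has the same expectation in both arms and cancels in the first bracket. What is left is the treatment effect. Only precision, and the reading of within-arm change, can be affected.

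**3. Whether the two chamber sessions match.** They agree in duration and in the two measures. In section 8.3.1 the list after "CAE Exposure (90 minutes) with" is blank for Visit 3, and the corresponding list is blank for Visit 1, so assessment times and grading cannot be compared. The Visit 1 window is Day −14 −16/+2, that is Day −30 to Day −12. The in-office baseline is taken on Day 1, the day before the outcome. Nothing visible establishes which of the two predicts the Day 2 CAE better.

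**4. How large the gain could be.** The plan has no figure to reproduce: effect, SD, power and correlations for these endpoints are all withheld. Everything below is assumed, apart from the alpha level ("All analyses will be 2-sided at a significance level of 0.05") and n = 350/2 = 175 per arm from the approximate enrolment. (Section 4 also mentions about 150 per arm; given the assumed starting power, this does not alter the result.)

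Let a = correlation of the in-office value with the Day 2 CAE mean, b = correlation of the Visit 1 CAE mean with the Day 2 CAE mean, and c = correlation between the two predictors.

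- Residual variance with the in-office value only: 1 − a²
- With both: 1 − R², where R² = (a² + b² − 2abc)/(1 − c²)
- Variance factor: F = (1 − R²)/(1 − a²)
- Power from an assumed 80%: Φ(2.80/√F − 1.96)

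| a | b | c | R² | F | Power |
|---|---|---|---|---|---|
| 0.5 | 0.6 | 0.5 | 0.31/0.75 = 0.413 | 0.587/0.75 = 0.78 | about 89% |
| 0.5 | 0.7 | 0.5 | 0.39/0.75 = 0.52 | 0.48/0.75 = 0.64 | 93.8% |
| 0.5 | 0.5 | 0.5 | 0.25/0.75 = 0.333 | 0.667/0.75 = 0.89 | 84.4% |
| 0.5 | 0.3 | 0.5 | 0.19/0.75 = 0.253 | 0.747/0.75 = 0.996 | 80.2% |
| 0.7 | 0.5 | 0.7 | 0.25/0.51 = 0.490 | 0.510/0.51 = 1.00 | 80.0% |

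With each correlation at 0.3, 0.5 or 0.7, F runs from 0.48 to 1.00 and power from 80% to 98%. If the Visit 1 CAE is assumed to be the better predictor (b of 0.6 to 0.7, with a and c of 0.3 to 0.5), the variance cut is 22% to 45%. That gain follows from the assumed ordering, which the documents do not support. If Visit 1 CAE scores also helped to select subjects (an assumption; no such criterion is visible), keeping the top 350 of the roughly 600 screened would shrink a correlation of 0.5 to about 0.35 and one of 0.7 to about 0.53.

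**5. Cost of the covariate.** With no predictive value it costs one degree of freedom: (350 − 3)/(350 − 4) = 1.003, or about 0.3% in variance.

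**The case for a change.** The best case on the other side is that adjustment is nearly costless and potentially valuable. The covariate is measured before randomization, so it cannot introduce post-treatment bias. It needs no new data, its cost is about 0.3% of variance, and under favourable correlations it adds more than ten points of power to tests that gate the rest of the sequence. The only baseline rule on view passes over the Visit 1 CAE, and no endpoint-specific baseline is visible.

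All of that stands as an argument for including the covariate. It does not show that the plan excludes it. Choosing the in-office value to compute change is compatible with a model that also adjusts for the Visit 1 CAE mean or time-matched values. A further premise, that tests 3 and 4 are the only confirmatory tests of redness and symptoms under challenge, cannot be confirmed either: the numbered list in 10.4.4 breaks off into fragments after its fifth item.

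**Conclusion.** The concern does not hold. The visible text supports the setting: an in-office Day 1 baseline, and an untreated 90-minute CAE at Visit 1 with dryness and redness recorded. It does not support the operative claim that the Visit 1 CAE is left out of the analysis, because the model text is withheld and the governing SAP is not in the public file.

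The comparison with vehicle is unbiased whichever baseline is used. Any gain from the extra covariate lies between nothing and a substantial amount (variance factor 1.00 down to 0.48 on the grid tried; 0.89 with all three correlations at 0.5). Those figures rest on assumed correlations, an assumed 80% starting power and a comparison model that already adjusts for the in-office value, none of which the documents give. A reader with the full SAP can settle in one look whether the Visit 1 CAE enters the models for these two endpoints. On the documents available there is no contradiction, bias or demonstrated loss.

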# **6.4** Exploratory Endpoints

- Change in tear RASP levels before and after Dose 1 and 2 on Day 1 and Dose 3 on Day 2
- Conjunctival redness, and visual analog scale dryness score by time point during the CAE

#### 7 STUDY MATERIALS

# 7.1 Study Treatment(s)

#### 7.1.1 Formulations

Randomized Study Treatments

- 0.25% Reproxalap Ophthalmic Solution
- Vehicle

# 7.1.2 Study Drug Packaging Configuration

[figure not shown]
# 7.1.3 Study Drug Storage and Accountability

The study drug must be stored in a secure area accessible only to the investigator and his/her designees. The study drug will be administered only to subjects entered into the clinical study, in accordance with the conditions specified in this protocol.

The study drug is to only be prescribed by the principal investigator or his/her named sub investigator(s), and is to only be used in accordance with this protocol. The study drug must only be distributed to subjects properly qualified under this protocol to receive study drug. The investigator must keep an accurate accounting of the study drug by maintaining a detailed inventory. This includes the amount of study drug received by the site, amount used, and the amount returned to the Sponsor upon the completion of the study.

#### 7.1.4 Instructions for Dispensation, Use, and Administration

Confidential Page 23 of 60

## 7.2 Other Study Supplies

Tear collection supplies, Schirmer's Test strips, Scale to weigh Schirmer's strips, 2% preservative-free sodium Fluorescein Solution, Fluorescein Strips, ETDRS Series 2000 Chart 1 & Chart 2, eye occluder, alcohol swabs.

#### 8 STUDY METHODS AND PROCEDURES

#### 8.1 Subject Entry Procedures

#### 8.1.1 Overview

Subjects as defined by the criteria in section 5.2, 5.3, and 5.4 will be considered for entry into the trial.

#### 8.1.2 Informed Consent

Prior to each subject's participation in the clinical trial (i.e., changes in a subject's medical treatment and/or study related procedures), the clinical trial will be discussed with the subjects, and subjects wishing to participate must give written informed consent using an informed consent form. The informed consent form must be the most recent version that has received approval/favorable review by a properly constituted Independent Review Board.

#### 8.1.3 Washout Intervals

Prohibited medications, treatments, and activities are outlined in the exclusion criteria.

#### 8.1.4 Procedures for Final Study Entry

Subjects must satisfy all of the inclusion criteria and none of the exclusion criteria in order to be entered into the study.

Confidential Page 24 of 60

#### 8.1.5 Methods for Assignment to Treatment Groups:

At Visit 1 each subject who signs the informed consent will be assigned a screening number. All screening numbers will be assigned in strict numerical sequence at each site and no numbers will be skipped or omitted.

At Visit 2, a patient who meets all the eligibility criteria will be randomized to receive reproxalap or vehicle in a 1:1 ratio. Patients will be assigned a randomization number and kit number via IWRS.

Both the randomization number and the assigned study drug kit number will be recorded on the patient's source document and eCRF.

# **8.2** Concurrent Therapies

The use of any applicable concurrent medications, prescription or OTC medications is to be recorded on the subject's source document along with the reason the medication was taken.

Concurrent enrollment in an investigational drug or medical device study is not permitted.

#### 8.2.1 Prohibited Medications/Treatments

Prohibited medications, treatments, and activities are outlined in the exclusion criteria.

#### 8.2.2 Escape Medications

Not applicable.

#### 8.2.3 Special Diet or Activities

Not applicable.

#### **8.3** Examination Procedures

# 8.3.1 Procedures to be Performed at the Study Visit with Regard to Study Objective(s)

#### Visit 1 (Day -14 -16/+2, Screening)

- Informed Consent and HIPAA
- Demographics (e.g., gender, date of birth, race, ethnicity)
- Medical/Medication & Ocular History
- Urine Pregnancy Test (as needed)
- Symptom Questionnaires:

Confidential Page 25 of 60

- Ocular Dryness Visual Analog Scale
- Visual Acuity (ETDRS)
- Slit Lamp Biomicroscopy with Conjunctival Redness assessment
- Fluorescein Staining
- Inclusion/Exclusion Criteria Review
- \_\_\_\_
- CAE Exposure (90 minutes, with:
- Slit Lamp Biomicroscopy with Conjunctival Redness assessment
- Schirmer's Test
- Intraocular Pressure
- Dilated Exam
- Schedule for Visit 2

#### Visit 2 (Day 1, Baseline and In-Office Dosing)

- Medical/Medication Update
- Adverse Event Query
- Visual Acuity (ETDRS)
- Slit Lamp Biomicroscopy
- Symptom Questionnaires
- Conjunctival Redness Photography
- Inclusion/Exclusion Criteria Review
- Randomization/Enrollment
- Pre-Dose #1 Tear Collection (30 +/- 5 minutes pre-dose)
- In-Office Dose #1
- Post-Dose #1 Tear Collection (started within 10 + 2 minutes of dose) *Wait 3 hours between doses*

Confidential Page 26 of 60

- Pre-Dose #2 Tear Collection (30 +/- 5 minutes pre-dose)
- In-Office Dose # 2
- Post-Dose #2 Tear Collection (started within 10 + 2 minutes of dose) Wait 30 minutes between doses
- In-Office Dose #3
- Conjunctival Redness Photography (10 minutes +/- 2 minutes post-Dose #3)
- Symptom Questionnaires started within 10 minutes + 2 minutes post-

Wait 30 minutes between doses

- Pre-Dose #4 Schirmer's Test (10 +/- 2 minutes pre-dose)
  - Weigh Schirmer's Test strip before and after use
- In-Office Dose #4
- Post-Dose #4 Schirmer's Test (started within 5 +/- 2 minutes of dose)
  - Weigh Schirmer's Test strip before and after use
- Schedule for Visit 3

# Visit 3 (Day 2, CAE■)

- Medical/Medication Update
- Adverse Event Query
- Urine Pregnancy Test (as needed)
- Visual Acuity (ETDRS)
- Slit Lamp Biomicroscopy
- Conjunctival Redness Photography
- Symptom Questionnaires:

- Pre-Dose #1 Tear Collection (30 +/- 5 minutes pre-dose)
- In-Office Dose #1 within 10 minutes prior to CAE Entry
- CAE Exposure (90 minutes) with:

Confidential Page 27 of 60

- In-Office Dose #2 (45 +/- 2 minutes into CAE exposure, administer by site staff)
- Post-CAE exit Tear Collection (started within 5 + 2 minutes)
- In-Office Dose #3 (started within 2 minutes post-tear collection)
- Symptom Questionnaires started within 10 minutes + 2 minutes post-Dose #3:

- Post-Dose #3 Tear Collection (started within 15 + 2 minutes of dose)
- Slit Lamp Biomicroscopy
- Intraocular Pressure
- Dilated Exam
- Study Exit

#### **Early Termination/Discontinuation**

If a subject is discontinued from the study prior to Visit 3, then all safety evaluations that are to be performed at Visit 3 should be performed on the day of discontinuation (early termination) or at the discretion of the investigator.

Adverse Events (both elicited and observed) and serious adverse events (SAEs) will be monitored throughout the trial. The investigator will promptly review all adverse events (both elicited and observed) for accuracy and completeness. All adverse events will be documented on the appropriate source document and case report form.

If a female reports a pregnancy or has a positive pregnancy test during the study the investigator will notify immediately. The investigator shall request from the subject and/or the subject's physician copies of all related medical reports during the pregnancy and shall document the outcome of the pregnancy. The investigator will retain these reports together with the subject's source documents and will provide a copy of all documentation to . The pregnant subjects will be discontinued from the trial as per the exclusion criteria.

#### 8.4 Schedule of Visits, Measurements and Dosing

#### 8.4.1 Scheduled Visits

Refer to Appendix 1 for a schedule of visits and measurements.

Confidential Page 28 of 60

#### 8.4.2 Unscheduled Visits

These visits may be performed in order to ensure subject safety. All procedures performed at an unscheduled visit will be recorded in the source documents and on the Unscheduled Visit eCRF pages. Any procedure indicated in the eCRF that is not performed should be indicated as "Not done."

Evaluations that may be conducted at an Unscheduled Visit include:

- Slit-lamp Biomicroscopy;
- Visual Acuity;
- Intraocular Pressure;
- Urine Pregnancy Test;
- Dilated Fundoscopy;
- Assessment of Adverse Events;
- Assessment of concurrent medications and/or treatments; and
- Any other assessments needed in the judgment of the investigator.

# 8.5 Subject Disposition

#### 8.5.1 Completed Subjects

A completed subject is one who has not been discontinued from the study and has completed all applicable assessments.

#### 8.5.2 Discontinued Subjects

Subjects may be discontinued prior to their completion of the study due to:

- adverse events
- protocol violations
- administrative reasons (e.g., inability to continue)
- Sponsor termination of study
- other

Note: In addition, any subject may be discontinued for any sound medical reason.

Notification of a subject discontinuation and the reason for discontinuation will be made to and will be clearly documented on the source document.

Confidential Page 29 of 60

#### 8.6 Study Termination

The clinical trial may be stopped at any time by the investigator, or with appropriate notification.

# 8.7 Study Duration

An individual subject's participation is estimated to be approximately 2-4 weeks.

#### 8.8 Monitoring and Quality Assurance

During the course of the study a monitor, or designee, will make routine site visits to review protocol compliance, assess study drug accountability and storage conditions, subject safety, and ensure the study is being conducted according to the pertinent regulatory requirements. The review of the subjects' medical records will be performed in a manner that adequately maintains subject confidentiality. Further details of the study monitoring will be outlined in a monitoring plan.

Regulatory authorities of domestic and foreign agencies, quality assurance and or its designees may carry out on-site inspections and audits which may include source data checks. Therefore, direct access to the original source data will be required for inspections and audits. All inspections and audits will be carried out giving consideration to data protection as well as subject confidentiality to the extent that local, state, and federal laws apply.

